PROTOCOL AMENDMENT #1

LCCC1950: RITUXIMAB FOR MULTICENTRIC CASTLEMAN DISEASE IN MALAWI, A SINGLE-ARM PHASE II SAFETY/EFFICACY TRIAL

AMENDMENT INCORPORATES (check all that apply):

Editorial, administrative changes
 Scientific changes (IRB approval)
 Therapy changes (IRB approval)
 Eligibility Changes (IRB approval)

The primary purpose of this protocol amendment is to update the secondary and exploratory objectives, clarify the timing of screening evaluations and assessments, amend the eligibility criteria, and clarify the determination of subject risk classification based on anemia. Specifically, the protocol now lists several secondary objectives separately for clarity. Additionally, an exploratory objective has been added to evaluate predictors of relapse or refractory disease with rituximab-based treatment. Secondary and exploratory endpoints were also added or reordered for completeness and clarity and to accompany the new exploratory objective. Furthermore, the protocol was reviewed and edited for consistency while also updating key personnel.

Editorial/Administrative

1. Mechanical edits made where appropriate.
2. Co-investigator list removed.
3. Biostatistician contact information added.
4. List of abbreviations updated.
5. Section 11.3 Honest broker language updated.
6. Appendix E (ECOG Performance Status) added.

Scientific

1. In Section 2.2:
 - a. Secondary objectives for overall survival, event-free survival, and Kaposi sarcoma viral load (2.2.2, 2.2.3, and 2.2.11) were listed separately for clarity.
 - b. Secondary objectives 2.2.4 and 2.2.5 were clarified by including the time at which clinical response rates and radiologic response rates, respectively, will be assessed.
2. In Section 2.3: An additional exploratory objective to evaluate for predictors of relapse or refractory disease with rituximab-based treatment was added (2.3.3).
3. Section 3.2: Secondary endpoints added or amended to ensure each secondary objective had a corresponding description of the endpoint (3.2.1 – 3.2.5, and 3.2.9). This included reordering and/or listing separately endpoints already present in the section.

4. Section 3.3: Exploratory endpoints added for all exploratory objectives (3.3.1-3.3.3).
5. Study Schema (Section 5.1) footnotes updated to clarify risk classification.
6. Statistical considerations (Section 10.1) updated to clarify risk classification.

Therapeutic

1. Prohibited medications/treatments (Section 5.5) updated to prohibit systemic therapies for other active malignancies or active infections.
2. Quality of Life assessments extended to 24 months after the end of treatment.
3. The timing of correlative testing blood sample draws was clarified in section 7.4 and the T&E table (Section 8.0).
4. T&E table updates:
 - a. Adjustments were made to ensure all timepoints are calculated from the start of treatment.
 - b. Follow-up visit specified at 12 weeks for consistency with objectives and endpoints.
 - c. Long term follow up column added for clarity.
 - d. Correlative blood draws combined into one row for clarity.
 - e. Rows for tumor biopsy, survival, and treatments added for completeness.
 - f. Footnotes updated to reflect other updates made throughout the protocol and to capture additional information (see #6 below).
5. CD4 count and HIV viral load long term follow up timepoints updated to 12 and 24 months for subjects that are HIV positive.
6. Sections 8.2 through 8.4.2 removed and where appropriate information moved to T&E.

Eligibility

1. Section 4.0 was clarified to specify that the allowable screening evaluation window prior to enrollment is 21 days.
2. Criterion 4.1.7 was amended to clarify qualifying anemia.
3. Criterion 4.1.9 was amended to extend the time that breastfeeding is prohibited after treatment.
4. Criterion 4.1.10 was amended to extend the time that birth control should be taken by females after treatment.
5. Criterion 4.1.11 was amended to extend the time that birth control should be taken by males after treatment.
6. Criterion 4.1.12 was added to address the conditions of corticosteroid use
7. Criterion 4.2.7 was amended to clarify the conditions of corticosteroid use and the requirement of steroid washout prior to enrollment.
8. Criterion 4.2.11 was added to ensure pregnant and/or breastfeeding women are not enrolled.

THE ATTACHED VERSION December 20, 2021 INCORPORATES THE ABOVE REVISIONS

ATTACH TO THE FRONT OF EVERY COPY OF PROTOCOL

**LCCC 1950: RITUXIMAB FOR MULTICENTRIC CASTLEMAN DISEASE IN
MALAWI, A SINGLE-ARM PHASE II SAFETY/EFFICACY TRIAL**

Short Title: Safety and efficacy of rituximab for treatment of multicentric Castleman disease in Malawi

Principal Investigator

[name]
[name]
[name]
[name]
[REDACTED]

Email: [contact]

Biostatistician

[name]
UNC Project, Tidziwe Centre
[name]
Lilongwe, Malawi

1.0 BACKGROUND AND RATIONALE

1.1 Study Synopsis

In sub-Saharan Africa (SSA), Kaposi sarcoma herpesvirus (KSHV)-related cancers account for 10-35% of malignancies¹⁻³ and >10% of cancer-related deaths.³ Multicentric Castleman disease (MCD) is a life-threatening lymphoproliferative disorder characterized by systemic inflammation and lymphadenopathy. MCD is strongly associated with KSHV and human immunodeficiency virus (HIV). KSHV seroprevalence in SSA is >40%,^{4,5} the highest of any region in the world; likewise, the prevalence of HIV is high.⁶ Substantial knowledge gaps remain regarding treatment for MCD, including outcomes, safety, and cost-effectiveness, particularly in SSA.

MCD can be controlled with chemotherapy. When chemotherapy is discontinued, however, rapid relapses or development of non-Hodgkin lymphoma (NHL) occur with high mortality.^{7,8} Long-term remission is achieved in most patients with rituximab, an anti-CD20 monoclonal antibody, as described in small clinical trials in high-income countries (HIC).⁹⁻¹¹ However, rituximab has not been evaluated for MCD in SSA, nor are there published safety data for rituximab from the region.

In this study, we aim to determine the safety and efficacy of first-line, risk-stratified rituximab-based MCD treatment in Malawi in a single-arm, phase II clinical trial. We will enroll 27 subjects with newly diagnosed or previously treated MCD (who have not previously received rituximab) requiring treatment (B symptoms or hemoglobin <10 g/dL).¹² Subjects will be treated with four weekly doses of rituximab. High-risk subjects (defined as patients with Eastern Cooperative Oncology Group (ECOG) performance status >2 or hemoglobin <8 g/dL)^{9,10,13-16} will also receive etoposide chemotherapy.^{9,11} Subjects will be followed for one year for toxicity and two years for survival. The primary outcome will be safety, defined as the frequency of \geq Grade 3 treatment-related Common Terminology Criteria for Adverse Events (AEs). Secondary outcomes will be event-free survival (death, progression, or development of NHL) and 1- and 2-year overall survival (OS). We also aim to compare the cost-effectiveness of first-line rituximab treatment for MCD in Malawi to chemotherapy (using our historical controls).

1.2 Multicentric Castleman Disease

MCD is a unique, life-threatening lymphoproliferative disorder characterized by systemic inflammation and lymphadenopathy that is strongly associated with KSHV and HIV. KSHV viral proteins, including a viral homolog of interleukin-6 (IL-6), are causally associated with the cytokine storm that is characteristic of MCD. HIV-infection is also a significant risk factor for MCD. In a large MCD cohort in France, 83% of MCD cases occurred in HIV-infected individuals.¹⁷ MCD consists of two biologically-distinct subtypes: KSHV-associated and idiopathic. This proposal focuses on KSHV-associated MCD, the variant that is far more common in SSA.¹⁸

KSHV seroprevalence is >40% in SSA,^{4,5,19} the highest of any region in the world (Figure 1). KSHV is usually transmitted through saliva with primary infection being asymptomatic. In some cases, KSHV is reactivated in a lytic state which can promote development of malignancies.²⁰ In Malawi, KSHV prevalence is 54% in adults and 74% in HIV-infected adults.²¹

[figure not shown]

Figure 1. Seroprevalence of Kaposi sarcoma-associated herpesvirus. The prevalence in Sub-Saharan Africa generally, and Malawi specifically, are amongst the highest in the world.

The burden of HIV is likewise high in SSA, ranging from 3-20%.⁶ The prevalence of HIV among adults in Malawi is 10%. The last decade has seen major strides in scale-up of anti-retroviral therapy (ART) in SSA, and it is now estimated that 67% of HIV-infected individuals in Malawi are on ART and 59% are virologically suppressed.²²

Given the strong link to KSHV and HIV, and high prevalence of these viruses in SSA, MCD is likely underdiagnosed in SSA. The under-diagnosis of MCD is likely due to limited pathology services and limited awareness of MCD. However, regional centers have recently reported MCD diagnoses in SSA.^{23,24} In our prospective cohort of lymphoproliferative disorders in Malawi, we have found that MCD constitutes 25/360 (7%) of all diagnoses and 25/189 (13%) of diagnoses among HIV-infected subjects.^{8,25-27}

MCD burden in SSA will likely increase as ART access expands and life expectancy of HIV-infected subjects improves. MCD is associated with older age, higher CD4 count, and longer time on ART compared to KS,^{9,17,28} NHL, or Hodgkin lymphoma.²⁶ Unlike KS, MCD is not controlled with ART alone.²⁹

1.3 Rituximab

Rituximab, an anti-CD20 monoclonal antibody, induces long-term remissions and decreases the risk of NHL in small clinical trials for MCD in HIC.^{9,10,16,30} Rituximab is a chimeric monoclonal antibody against CD20, a protein on the surface of B-cells which leads to B-cell depletion via complement- and antibody-mediated cytotoxicity. In two phase II trials of single-agent rituximab for MCD, the one-year event-free survival (EFS) was 92% and 71%.^{10,15} After longer follow-up, five-year EFS was 78% and five-year OS was 88%.³¹ Likewise, rituximab has been shown to significantly decrease the risk of NHL.^{9,30,31}

Mortality often occurs in the first month of treatment with rituximab monotherapy, but this risk can be mitigated with concomitant chemotherapy. Death in the first four weeks occurs in 5% of MCD subjects treated with rituximab alone.^{10,13-15,31} Risk factors for early death include ECOG performance status >2, hemophagocytic syndrome, and severe hemolytic anemia. The risk of death decreases with the addition of etoposide⁹ or liposomal

doxorubicin.¹⁶ Among subjects with MCD and pre-existing KS, the risk of KS exacerbation following rituximab monotherapy is 36-75%.^{9,10} However, death from KS progression is rarely reported.

Rituximab has not been evaluated as first-line therapy for MCD in SSA. Given high opportunistic infection burden and limited supportive care infrastructure in SSA, region-specific safety and efficacy data for rituximab are needed. When added to combination chemotherapy for NHL in HIC, rituximab has been associated with an increase in treatment-related infections and mortality in HIV-infected subjects with a CD4 count <50 cells/ μ l, while benefiting those with higher CD4 counts.^{32,33} Rituximab-based treatment +/- etoposide is likely to be less toxic than combination chemotherapy, but requires formal safety assessment. Previous studies of rituximab for MCD from HIC have found a rate of non-hematologic \geq Grade 3 AEs of around 20%.^{9,10,15,16}

Even if rituximab is safe and effective, cost-effectiveness is a critical consideration. The World Health Organization (WHO) lists rituximab as a complementary medicine on the Essential Medicines list.³⁴ However, rituximab has not been approved for routine use by the Malawi Pharmacy, Medicines, and Poisons Board and is not routinely available in Malawi, like most public sector health systems in SSA. Cost-effectiveness analysis done in the appropriate, local context is essential to help policymakers allocate limited health resources.³⁵ To our knowledge, such analyses have not been published but are urgently needed. A demonstration of cost-effectiveness would support the prioritization of rituximab as a sound public health investment to treat this emerging HIV-associated comorbidity.

1.4 Etoposide

Etoposide is a topoisomerase II inhibitor that causes DNA double strand breaks and apoptosis of rapidly dividing cells, especially cancer cells. Etoposide is a common chemotherapeutic agent used in the treatment of a number of neoplasms, including lymphoma, KS, testicular cancer, Ewing sarcoma, and small cell lung cancer, among others. It is often given in combination with other chemotherapies but when given as monotherapy, etoposide is commonly associated with a number of AEs. Common AEs include alopecia, constipation, diarrhea, anemia, thrombocytopenia, leukopenia, and infusion reactions (either local site reactions or hypotension). Less common AEs include nausea, vomiting, rash, fever, and mouth sores. Rare but serious AEs include secondary malignancies, especially acute myeloid leukemia.

Etoposide pharmacokinetics

After intravenous (IV) injection, there is a biphasic pattern of clearance with a terminal $t_{1/2}$ of about 6–8 hours in patients with normal renal function. Approximately 40% of an administered dose is excreted intact in the urine. In patients with compromised renal function, dosage should be reduced in proportion to the reduction in creatinine clearance. In patients with advanced liver disease, increased toxicity may result from a low serum albumin (decreases drug binding) and elevated bilirubin (displaces etoposide from albumin); guidelines for dose reduction in this circumstance have not been defined.

Etoposide for Kaposi sarcoma in SSA

Etoposide has been used successfully as a single-agent treatment for KS, including in SSA.³⁶ However, other regimens have recently been shown to be superior to etoposide for KS treatment in SSA.³⁷ In the ACTG5264/AMC-067 trial of up-front versus as-needed etoposide for KS in SSA, the rate of \geq Grade 3 AEs was 50% in the up-front group versus 44% in the as-needed group. The majority of AEs were hematologic (47/65; 72%). There were no study-related deaths. That study was conducted with oral etoposide 50-100 mg daily days 1-7 of 14-day cycles but provides the best evidence for treatment in HIV-infected patients in SSA.

Etoposide for MCD

A more relevant study by Bower, et al⁹ used a similar risk-adapted treatment for MCD and used IV etoposide at 100 mg/m². The study was not prospective and reported very limited data on AEs. No study-related deaths were identified in patients receiving etoposide. The rate of KS progression among those with baseline KS was 9/24 (38%) and did not differ between those who received etoposide + rituximab or rituximab alone. In this protocol, we similarly propose the use of IV etoposide at 100 mg/m².

1.5 Rationale for Clinical Study

MCD can be treated with chemotherapy. Many single-agent or combination chemotherapies have been utilized.^{7,8,29,38} However, when chemotherapy is discontinued, rapid relapses or development of NHL often occur and are associated with high mortality.^{7,8,38} Relapse after termination of chemotherapy is almost universal, and 1-year EFS is <20%.^{7,8} 15-25% of subjects treated with chemotherapy develop NHL, a rate ~15x higher than HIV-infected individuals without MCD.^{17,29,39} Survival for MCD subjects treated with traditional chemotherapy is also poor with 2-year OS of 42% in one study.⁹

Similarly, outcomes for MCD subjects treated with chemotherapy in Malawi are also poor. Of the 25 MCD patients in our cohort, 2 died before starting chemotherapy. Of 23 patients treated with chemotherapy, only 3 (13%) remain in remission after 5, 13, and 15 months respectively, similar to reports from HIC. First-line chemotherapy consisted of etoposide (17 patients) or cyclophosphamide, vincristine, and prednisone (six patients). Among 23 treated patients, 10 (43%) completed first-line chemotherapy without disease progression. The remaining 13 patients were switched to an alternative therapy because of poor response. Of the ten patients who completed first-line treatment, seven relapsed, after a median 29 days (range 14-147). One-year EFS was 10% (95% CI 2-26) (**Figure 2; Panel A**).

Rituximab has been successfully used by our group in Malawi as a compassionate-use intervention for patients with MCD refractory to chemotherapy, and in an ongoing clinical trial for diffuse large B cell lymphoma (DLBCL). As in most SSA public health systems, rituximab is not currently approved nor available in Malawi. With support from the University of North Carolina (UNC) Lineberger Comprehensive Cancer Center (LCCC), we are currently evaluating rituximab plus cyclophosphamide, vincristine, doxorubicin, and prednisone (CHOP) chemotherapy for DLBCL (NCT02660710), with 39 of 40 patients enrolled as of September 2019. To date, there have been 19 non-hematologic Grade 3 or worse AEs, and 1-year OS is 70%, which compares favorably to our previous work evaluating a historical cohort of patients treated with CHOP.⁴⁰

Given high mortality, absent alternative therapies for such patients, and the availability of rituximab from this trial, we sought a compassionate use exemption from Malawi regulatory authorities to treat patients with MCD refractory to chemotherapy. As of January 2019, ten patients have received rituximab as salvage therapy for MCD. There was one Grade 3 hypersensitivity reaction but no other serious AEs. Early clinical outcomes have been encouraging. Among these 10 patients, 9 achieved remission and 7 remain in remission after a median 7 months (range 1-22). Only one patient who received rituximab died (MCD progression). One-year EFS after receiving rituximab for relapsed/refractory MCD was 78% (95% CI 37-94) (**Figure 2; Panel B**).

1.6 Correlative Studies

Core biopsy specimens taken for routine diagnostic purposes will be used to make formalin-fixed paraffin embedded tissue blocks without any additional research biopsies. These specimens will allow for viral and genomic investigations. Gene expression

[figure not shown]

Figure 2. Event-free survival for MCD patients in Malawi treated with A) first-line chemotherapy and B) salvage rituximab.

profiling and next-generation sequencing analyses of histopathologically confirmed MCD specimens only will be conducted at the UNC Genome Analysis Facility and the UNC High-Throughput Sequencing Facility in North Carolina. Viral sequencing will be conducted by the UNC Vironomics Core. These studies will not influence treatment for enrolled patients in real time, as 'targeted' cancer therapies are not currently available in Malawi. Rather, we intend to examine the expression signature of MCD with respect to specific genes which are clearly established as influencing phenotypic clinical behavior of lymphomas, including genes involved in lymphocyte proliferation, activation, and differentiation, as has been previously extensively described in seminal papers in the field.^{27,28}

Though extensive studies have been conducted in lymphoma, little is known about gene expression profiles in patients with MCD. These experiments are intended to identify mechanisms of, and risk factors for, development of MCD. Cryopreserved serum obtained at enrollment and prespecified follow-up visits only will be stored to allow basic correlative studies of predictive and prognostic biomarkers in a setting where advanced imaging for lymphoma response assessment after treatment is not available. These samples will be used for cytokine and immunologic profiling of patients with MCD. MCD is a polyclonal disease that develops in the setting of immune dysregulation but the immunologic mechanisms of this dysregulation have not been well established.

Furthermore, if certain cytokines are found to be of special significance in the pathophysiology of MCD in HIV-infected patients, cytokine-targeted therapies may be employed in future studies to treat this disease with decreased side effects, as has been completed previously in idiopathic MCD.⁴¹ Such treatments are likely to be safer and more effective than conventional cytotoxic therapy in the Malawian context, where supportive care including hematopoietic growth factors and transfusion support are extremely limited, and where infectious burden is high.⁴ Genomic data will be analyzed by study investigators including Malawian colleagues, with bioinformatics support additionally provided from UNC-Chapel Hill as necessary.

2.0 STUDY OBJECTIVES

2.1 Primary Objectives

2.1.1 To determine the safety and treatment related mortality of a risk-adjusted treatment protocol for the treatment of MCD with rituximab with or without etoposide in Malawi.

2.2 Secondary Objectives

2.2.1 To prospectively characterize MCD presentation in Malawi.

2.2.2 To determine overall survival rate.

2.2.3 To determine event-free survival rate.

2.2.4 To describe the efficacy of the risk-adjusted treatment protocol as determined by clinical response rates at end of treatment and 12 weeks after start of treatment.

2.2.5 To describe radiologic response rates at end of treatment and 12 weeks after start of treatment.

2.2.6 To further characterize the safety by describing the frequency of all AEs with risk-adjusted treatment-protocol for MCD in Malawi.

2.2.7 To describe the rate of Kaposi sarcoma exacerbation, as defined by symptomatic or clinical (dermatologic or visceral organ) exacerbation of disease in patients receiving the risk-adjusted treatment protocol.

2.2.8 To describe the quality of life of patients with MCD before, during and after treatment with a rituximab-based, risk-adjusted treatment protocol, as assessed by the MCD symptom score and PROs.⁴²

2.2.9 To describe the trends in hemoglobin, platelet count, C-reactive protein (CRP), and IL-6 before, during, and after a risk-adjusted, rituximab-based treatment protocol

for MCD in Malawi and describe the utility of these markers as a predictor of relapse.

2.2.10 To evaluate for predictors of relapse or refractory disease with a risk-adjusted, rituximab-based treatment protocol.

2.2.11 To evaluate changes in Kaposi sarcoma viral load as a result of treatment.

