3.2 Secondary Endpoints

3.2.1 At study entry, basic demographics and baseline laboratory values will be summarized using descriptive statistics (i.e., means, medians, and variability measures for continuous variable; rates and proportions for binary variables). Screening assessments to be completed within 21 days prior to study enrollment.

3.2.2 Overall survival will be assessed at 12 weeks, one year, and two years from the start of treatment.

3.2.3 Event-free survival will be defined as the rate of refractory disease, relapse (same definition of active disease as in the inclusion criteria in section 4.1), non-Hodgkin lymphoma development or death and will be assessed at 12 weeks, one year, and two years from the start of treatment.

3.2.4 Clinical response rate at end of treatment and 12 weeks from treatment initiation (clinical response defined as resolution of presenting signs/symptoms that defined

the Multicentric Castleman disease (MCD) attack) without relapse at 12 weeks. MCD attack/flare is defined in Section 4.1.1.

3.2.5 Radiologic response rate is the percentage of patients without relapse at end of treatment and 12 weeks from treatment initiation. Chest radiography and abdominal sonography will be used for staging. Per Revised response criteria for gross lymphadenopathy, response will be evaluated via complete survey of lymph nodes with measurements and physical assessment of other palpable masses with measurements.

Response criteria for lymph node response will be as follows: Complete response (CR)- disappearance of all evident disease; Partial response (PR)-at least 50% decrease in target lesions with no increase in non-target lesions, Stable disease (SD)- Neither sufficient shrinkage to qualify for PR nor sufficient increase to qualify for progressive disease (PD); PD- appearance of a new lesion or at least a 50% increase in lesion size.

3.2.6 Additional safety assessment will be graded by CTCAE v 5.0 through 12 weeks from the start of therapy.

3.2.7 Kaposi sarcoma exacerbation will be defined as new symptoms attributed to KS or clinically evident exacerbation of dermatologic or visceral disease. All disease flares will be biopsy confirmed whenever possible.

3.2.8 Quality of life will be assessed by the MCD symptom score, a patient-reported outcomes questionnaire, and PROMIS Global 10, at baseline (week 1), 15 days (week 3), end of treatment (week 5), 12 weeks, 6 months, and 24 months after treatment, and at the time of any relapse.

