5.0 TREATMENT PLAN

5.1 Schema

[figure not shown]

Figure 4. Clinical trial schema for newly diagnosed patients with MCD requiring treatment.
"High-risk disease" defined as ECOG performance status >2 or hemoglobin <8 g/dL.

Clinical trial schema for newly diagnosed patients with MCD requiring treatment.

¹ "High-risk disease" defined as ECOG performance status >2 or hemoglobin <8 g/dL at the time of screening or enrollment labs. Note that a patient receiving a blood transfusion due to hemoglobin <8 g/dL within 1 month of enrollment will be considered high-risk.

² See Time and Events Table (8.1) for detailed study visit components.

³ MCD-SS=MCD symptom score

We will conduct a single arm, phase II clinical trial for safety and efficacy of risk-stratified treatment with rituximab +/- chemotherapy for MCD. Eligible patients will be enrolled and treated according to the study schema. High-risk patients (defined as patients with ECOG performance status >2 or hemoglobin <8 g/dL at the time of screening or enrollment labs)^{9,10,13-16} will receive four weekly doses of rituximab (375 mg/m²) and etoposide (100 mg/m²) as in Bower, et al.⁹ Low-risk patients will receive the same dose of rituximab alone.

The planned sample size is 27 patients and the primary outcome is safety. Secondary outcomes include one- and two-year EFS (combination of relapse, development of NHL, or death), OS, and KS exacerbation rates.

We will also collect clinical, laboratory, virologic data, and stored samples at baseline and end-of-treatment to both describe the presentation of MCD in our population and to evaluate risk factors for death or relapse.

Finally, we will conduct comprehensive microcosting analysis and a Markov model cost-effectiveness analysis.

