10.5 Secondary Objectives

10.5.1 To better characterize MCD presentation in Malawi.

Basic demographics and baseline laboratory values will be summarized using descriptive statistics (i.e., means, medians, and variability measures for continuous variable; rates and proportions for binary variables).

10.5.2 To describe the efficacy of the risk-adjusted approach as determined by clinical and radiologic response rates, 90-day, one-year, and two-year EFS and OS.

An event for EFS is either relapse (defined as “MCD attack” in the Inclusion Criteria (section 4.1)), refractory disease, lost-to-follow-up (LTFU), or death. We will consider patients LTFU if they cannot be contacted by phone for three months. Given the high mortality associated with MCD and previously published literature supporting a strong association between LTFU and mortality in SSA, we will consider LTFU as a failure event for both EFS and OS.⁴³ Relapse for purposes of this study will be defined as recurrence of an “MCD attack” (Inclusion Criteria; section 4.1) requiring re-initiation of treatment, with a strong preference for biopsy-proven recurrence whenever possible. We will conduct survival analysis using Kaplan-Meier methods. Radiologic response will be assessed in parallel with clinical response with response criteria defined in section 7.1.7. We will assess the prognostic value of radiologic response for EFS and OS in Cox proportional hazards model.^{10,15,16}

10.5.3 To describe the safety, as determined by the rate of all AEs during a risk-adjusted approach to treatment of MCD in Malawi.

All AEs will be described up to 30 days after final dose of MCD-directed treatment.

10.5.4 To describe the rate of KS exacerbation, as defined by symptomatic or clinical (dermatologic or visceral organ) exacerbation of disease.

The rate of KS exacerbation will be reported as the number of KS cases requiring KS-specific treatment divided by the number of patients with pre-existing KS (as defined by personal history of KS, baseline presence of KS, or KS in lymph node biopsy). This will be estimated along with a 95% confidence interval for the proportion.

10.5.5 To describe the quality of life of patients with MCD before, during and after treatment with a rituximab-based, risk-adjusted treatment approach, as assessed by the MCD symptom score⁴² and PROPr instrument.⁴⁴

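### The Kaposi sarcoma exacerbation rate in section 10.5.4 is a crude proportion with no time horizon and no rule for patients lost to follow-up, and its event differs from the one in 3.2.7

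*Combined protocol and SAP*

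**What the plan says.** Objective 2.2.7 reads: "To describe the rate of Kaposi sarcoma exacerbation, as defined by symptomatic or clinical (dermatologic or visceral organ) exacerbation of disease". Section 3.2.7 sets the event: "Kaposi sarcoma exacerbation will be defined as new symptoms attributed to KS or clinically evident exacerbation of dermatologic or visceral disease". Section 10.5.4 sets the estimator, which is narrower. The rate is "reported as the number of KS cases requiring KS-specific treatment divided by the number of patients with pre-existing KS", where pre-existing means a history of KS, KS at baseline, or KS in the node biopsy. On precision it adds: "This will be estimated along with a 95% confidence interval for the proportion".

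None of 2.2.7, 3.2.7 or 10.5.4 names a time point. The nearest hint is in section 5.1, repeated with small changes in 10.1: "Secondary outcomes include one- and two-year EFS (combination of relapse, development of NHL, or death), OS, and KS exacerbation rates". One can read the time words as covering the KS rates or as covering EFS alone.

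The only rule for loss to follow-up is in 10.5.2: "we will consider LTFU as a failure event for both EFS and OS". It rests on a stated association between loss and death in the region, and it does not mention KS.

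For background, section 1.3 says that, in patients with pre-existing KS, "the risk of KS exacerbation following rituximab monotherapy is 36-75" per cent. Section 1.4 gives 9/24 (38%) from a risk-adapted series. Neither figure has a stated horizon.

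**The concern.** KS exacerbation is a harm that the protocol singles out. Section 1.3 describes it, exclusion 4.2.1 is written to avoid it, and sections 5.1 and 10.1 list it among the main secondary outcomes. For a harm, an estimator that counts a patient lost alive as event-free errs in the favourable direction.

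Without a horizon, the same data can also give several different rates. The documents offer four windows for safety or follow-up:

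- 30 days after the last dose (9.2, 10.5.3)
- 12 weeks from the start of treatment (3.1, 3.2.6)
- one year for toxicity (1.1)
- 24 months of follow-up (5.8, Table 7)

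The neighbouring endpoints do fix their times: response at end of treatment and 12 weeks, and OS and EFS at 12 weeks, one year and two years. As written, the KS window could be chosen after the data are seen.

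**Working it through.** **Figures in the plan.** The KS endpoint has no sample size or precision statement to reproduce. Two related figures check: 24/(1 - 0.10) = 26.7, so 27 enrolled (10.2), and 9/24 = 37.5%, given as 38% (1.4; exact 95% interval 19 to 59%).

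**Inputs.** The true risks of 36% and 75% are the ends of the range in 1.3, and 50% is an assumed middle value. The 10% loss comes from 10.2, which applies it to the toxicity-monitoring period only. Any rate beyond that period is my assumption. The number of patients with KS is not given.

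**Step 1: steady loss.** Assume constant hazards, with λ for KS exacerbation and μ for loss while alive and still at risk, and leave deaths aside. The crude proportion at time T then has expectation λ/(λ+μ) × [1 - exp(-(λ+μ)T)], against a true risk of 1 - exp(-λT).

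Example at 12 weeks with a true risk of 36% and 10% lost: λT = -ln 0.64 = 0.446 and μT = -ln 0.90 = 0.105. The crude figure is 0.446/0.552 × (1 - 0.64 × 0.90) = 0.809 × 0.424 = 0.343.

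| Horizon and assumed loss | True risk | Crude figure | Shortfall (points) |
|---|---|---|---|
| 12 weeks, 10% lost | 36 / 50 / 75% | 34 / 48 / 72% | 1.7 / 2.3 / 3.0 |
| 1 year, 10% lost per year | 36 / 50 / 75% | 34 / 48 / 72% | 1.7 / 2.3 / 3.0 |
| 1 year, 10% lost per 12 weeks | 36 / 50 / 75% | 29 / 41 / 63% | 7 / 9 / 12 |
| 2 years, 10% lost per year | 59 / 75 / 94% | 54 / 69 / 88% | 5 / 6 / 6 |
| 2 years, 10% lost per 12 weeks | 59 / 75 / 94% | 41 / 54 / 73% | 18 / 21 / 20 |

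The two-year rows carry one-year risks of 36, 50 and 75% forward at the same hazard. Loss of 10% per 12 weeks implies 1 - 0.9^(52/12) = 37% lost by one year and 1 - 0.9^(104/12) = 60% by two years. The documents assume no such loss, so those rows are an upper scenario.

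**Step 2: all loss before any event can be seen.** The crude figure is then p × (1 - L). With L = 10%, 36% becomes 32% and 75% becomes 68%. With L = 30%, they become 25% and 53%. This is the unfavourable extreme for timing.

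**Step 3: dependence on the window.** Suppose 36% is the 12-week risk and later worsening that needs KS-specific treatment occurs at 5 to 20% per year (assumed). Then 1 - 0.64 × exp(-h(T - 12/52)) gives 38 to 45% at one year and 41 to 55% at two years.

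**Step 4: a small example.** Take 10 KS patients (hypothetical), with 3 events and 2 lost early.

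| Handling of the 2 lost | Rate | Exact 95% interval |
|---|---|---|
| Counted as KS-free, as in 10.5.4 | 3/10 = 30% | 7 to 65% |
| Left out | 3/8 = 38% | 9 to 76% |
| Counted as exacerbated | 5/10 = 50% | 19 to 81% |

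**Step 5: the two event definitions.** Under 3.2.7, new KS symptoms or visible worsening count whether treated or not. Under 10.5.4, only cases needing KS-specific treatment count. A month-20 worsening left untreated is an event under the first and not under the second.

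**The case against.** The strongest reply is that the crude proportion need not be biased. Keeping patients who die without exacerbation in the denominator is what a competing-risk estimate does. If lost patients are also taken to be dead, as 10.5.2 does for EFS and OS, nothing is left to censor, and at a fixed horizon the crude proportion equals the cumulative incidence. This stands for deaths, and for losses that really are deaths. It does not cover patients lost alive, and it still needs a fixed horizon, which 10.5.4 lacks.

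Other replies also stand in part. Carrying 10% per 12 weeks on to two years has no support in the documents. If flares cluster soon after rituximab, the constant-hazard model overstates the later bias. Under 10.5.4, late worsening counts only if it needs treatment. The endpoint is descriptive, and sampling error in a subset of 27 patients will far exceed 2 to 3 points.

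A reader might go further and infer that the result cannot be set against the 36-75% in section 1.3. The documents do not support that. The range has no stated horizon, no comparison with it is planned, and the 9/24 in section 1.4 is a simple proportion among patients with baseline KS, the same form as 10.5.4. Comparability is unclear, not excluded. The treated-cases numerator and the use of etoposide in high-risk patients, when the range is for monotherapy, also blur it.

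**Conclusion.** The point holds as a defect in a stated estimator. Section 10.5.4 counts patients lost alive as KS-free, leaves the window open, and uses a narrower event than 3.2.7. At 12 weeks the shortfall is about 2 to 3 points if 10% are lost evenly over time, and about 4 to 8 points if all of them are lost before any event could be seen. At one or two years it is material only if loss continues: 2 to 6 points at 10% per year, and more only under heavier loss. All of these sizes rest on assumed loss rates and on lost patients being alive with the same KS risk as those who stay.

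The 18-to-21-point figures in the working should not be read as the expected bias, because they need about 60% of patients to be lost by two years.

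The larger practical matter may be the open window and the two event definitions, which can each move the reported rate without any loss at all. The sample size and the primary safety conclusion are not affected.

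**What to change.** In 10.5.4, replace the proportion with the cumulative incidence of KS exacerbation among patients with pre-existing KS (Aalen-Johansen) at 12 weeks, one year and two years from the first dose, the times already set for EFS and OS. Treat death without exacerbation as a competing event, censor lost patients at last contact, and give 95% intervals.

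Since 10.5.2 links loss to death, censoring may be informative. Add two bounds: lost patients counted as exacerbated, and lost patients counted as competing deaths. With everyone else followed to the horizon, the second bound is the crude proportion at that time, so the planned figure remains as the lower end of a range.

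Reconcile 3.2.7 with 10.5.4 so that one event definition is used throughout, carry the time points into 2.2.7 and 3.2.7, and make the sentence in 5.1 and 10.1 say whether its times apply to KS.

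The cost is SAP wording, a few lines of analysis, and a minor eCRF field. Table 7 schedules concomitant medications only through end of treatment, and toxicity evaluation only through 12 weeks and again at 24 months, so dates of KS onset or treatment after week 5 may not be captured. History and examination already take place at every follow-up visit, and the date can be recorded there. Intervals will stay wide in a small subset.
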